**Note:**

- *Inadequate response is defined as failure to achieve and maintain remission or a low disease activity state (comparable to vIGA-ADTM 0=clear to 2=mild) despite treatment with a daily regimen of Topical corticosteroids (TCS) of medium to higher potency ( $\pm$  Topical calcineurin inhibitors (TCI) as appropriate), applied for at least 28 days or for the maximum duration recommended by the product prescribing information (e.g., 14 days for super-potent TCS), whichever is shorter.*
  - *Patients with documented systemic treatment for AD (for example systemic corticosteroids, cyclosporin) in the past 6 months are also considered as inadequate responders to topical treatments and are potentially eligible for treatment with DS107 after appropriate washout.*
  - *Important side effects or safety risks are those that outweigh the potential treatment benefits and include intolerance to treatment, hypersensitivity reactions, significant skin atrophy, and systemic effects, as assessed by the Investigator or by the patient's treating physician.*
12. Patients who are able to communicate well with the Investigator, to understand and comply with the requirements of the study, and understand and sign the written informed consent prior to initiation of any study specific activities or procedures.

### 7.3 Exclusion Criteria

1. Patients with other skin conditions that might interfere with AD diagnosis and/or evaluation (such as psoriasis or current active viral, bacterial and fungal skin infections) as assessed by the Investigator.
2. Patients who have used systemic treatments that could affect AD less than 4 weeks prior to baseline visit (Day 0), e.g. retinoids, methotrexate, cyclosporine, hydroxycarbamide (hydroxyurea), azathioprine and oral/injectable corticosteroids. Intranasal corticosteroids and inhaled corticosteroids for stable medical conditions are allowed.
3. Patient with previous exposure to DS107.
4. Patients who have used any topical medicated treatment for AD (except for emollients) two weeks prior to start of treatment/ Baseline (Day 0), including but not limited to, topical corticosteroids, calcineurin inhibitors, tars, bleach, antimicrobials and bleach baths.

5. Patients who use emollients containing urea, ceramides or hyaluronic acid less than twelve weeks prior to Baseline.
6. Patients who have had excessive sun exposure, have used tanning booths or other ultraviolet (UV) light sources four weeks prior to Baseline (Day 0) and/or are planning a trip to a sunny climate or to use tanning booths or other UV sources between screening and follow-up visits.
7. Patients who have a history of hypersensitivity to any substance in DS107 capsules or placebo capsules.
8. Patients who have a history of hypersensitivity to soy beans or soy lecithin.
9. Patients who have a white cell count or differential white cell count outside of the normal reference range at screening.

**Note:**

*For patients with a mild leucocytosis or leucopenia and otherwise a normal white cell blood count may be enrolled following consultation with the medical monitor by the investigator.*

10. Patients who have any clinically significant controlled or uncontrolled medical condition or laboratory abnormality that would, in the opinion of the Investigator, put the patient at undue risk or interfere with interpretation of study results.
11. Patients who have a clinically significant impairment of renal or hepatic function.
12. Patients with significant uncontrolled cardiovascular, neurologic, malignant, psychiatric, respiratory or hypertensive disease, as well as uncontrolled diabetes and floride arthritis or any other illness that, in the opinion of the Investigator, is likely to interfere with completion of the study.
13. Patients with active infectious disease (e.g., hepatitis B, hepatitis C or advanced disease secondary to infection with human immunodeficiency virus).
14. Patients with a history of clinically significant drug or alcohol abuse in the opinion of the Investigator in the last year prior to Baseline (Day 0).
15. Patients who have participated in any other clinical study with an investigational drug within 3 months before the first day of administration of study treatment.
16. Patients who have had treatment with biologics as follows:
  - a. Any cell-depleting agents including but not limited to rituximab: within 6 months before the screening visit, or until lymphocyte count returns to normal, whichever is longer,
  - b. Other biologics influencing cell proliferation: within 6 months before the screening visit.
  - c. Dupilumab or other monoclonal antibodies within 5 half-lives (if known) or 16 weeks prior to baseline visit, whichever is longer
17. Patients who are pregnant, planning pregnancy, breastfeeding and/or are unwilling to use adequate contraception (as specified in Inclusion Criterion 10) during the trial.
18. Patients, in the opinion of the Investigator, not suitable to participate in the study.

## 7.4 Screening and Consent

It is the responsibility of the Investigator, or a person designated by the Investigator (if acceptable to local regulation), to obtain written informed consent from each individual participating in this study after adequate explanation of the aims, methods, objectives and potential risks/benefits of the study. Patients will be given the opportunity to ask questions to the investigational team. It must also be explained to the patients that they are completely free to refuse to enter the study or to withdraw from it at any time for any reason. The patient will be given sufficient time to consider participation in the study. If, after this, the patient agrees to participate, they will be asked to sign and date one original copy of the written ICF. The patients will then receive a copy of the signed and dated patient information sheet (PIS)/ICF. The original signed ICF will be filed in the Investigator Site File (ISF). The PIS will contain site contact information in case of any questions or medical emergency.

If new safety information results in significant changes in the risk/benefit assessment or any new information presents that may affect willingness to continue to participate, the consent form should be updated and approved if necessary by the Research Ethics Board/Institutional Review Board. All patients (including those already being treated) should be informed of the new information, given a copy of the revised form and asked to give their consent to continue in the study. Any written information given to potential patients will be submitted to, and approved by, the respective Ethics Committee(s) (EC) prior to implementation.

The Investigator will maintain a Patient Screening Log to collect information on all patients who sign an ICF regardless of whether or not they meet the study eligibility criteria following completion of the screening evaluations. After completion of screening, all patients deemed eligible to take part in this study will be entered onto an Enrolment Log.

## 7.5 Withdrawal of Patients

Patients have the right to withdraw from the study at any time for any reason without penalty. The Investigator must explain this to the patient and that this will in no way prejudice their future treatment. The Investigator also has the right to withdraw patients from the study if he feels it is in the best interest of the patient or if the patient is uncooperative or non-compliant. It is understood by all concerned that an excessive rate of withdrawal can render the study uninterpretable, therefore, unnecessary withdrawal of patients should be avoided. Should a patient decide to withdraw, all efforts will be made to complete and report the observations, particularly the follow-up examination, as thoroughly as possible.

The Investigator or one of his or her staff members should contact the patient either by telephone or through a personal visit to determine as completely as possible the reason for the withdrawal, and record the reason in patient's source document and case report form (CRF). A complete final early termination evaluation at the time of the patient's withdrawal should be made with an explanation of why the patient is withdrawing from the study when ever possible. If the reason for removal of a patient is an adverse event or an abnormal laboratory test result, the principal specific event or test will be recorded. Patients who discontinue the study before Week 16/Visit 7 visit will be asked to come for an early termination visit as soon as possible and have the assessments listed at Week 16/Visit 7 performed. They will also be asked to return two weeks later for the safety assessments listed at Week 18/Visit 8.

Patients who develop Grade 3 or higher National Cancer Institute Common Terminology Criteria for Adverse Events (NCI-CTCAE), that is determined to be possibly or probably attributable to the study drug will be discontinued.

## **7.6 Patient Replacement**

Patients who are withdrawn from the study due to an adverse event or lack of effect will not be replaced. Patients who are withdrawn for other reasons (such as lost to follow up, personal reasons) may be replaced.

## **7.7 Protocol Violations**

All protocol violations will be reviewed by the Medical Monitor as and when each violation is detected. Based on this review a decision on the patient's continuation in the trial will be reached and this decision will be documented as appropriate. Notification will be made to the relevant authorities as required.

## **7.8 Stopping Criteria**

Trial will be stopped if more than one patient has a Grade 3 or higher AE on the CTCAE scale in any one category that is determined to be possibly or probably attributable to study drug.

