##### *Serious Adverse Events (SAE):*

If a patient experiences a serious adverse event after the first dose of the study drug, the event will be recorded as a serious adverse event.

*A serious adverse event (experience) or reaction is any untoward medical occurrence that at any dose:*

- results in death
- is life-threatening
- requires in-patient hospitalization or prolongation of existing hospitalization
- results in persistent or significant disability/incapacity, or
- is a congenital anomaly/birth defect

Note: The term "life-threatening" in the definition of "serious" refers to an event in which the patient was at risk of death at the time of the event. It does not refer to an event which hypothetically might have caused death if it were more severe.

Medical and scientific judgment should be exercised in deciding whether expedited reporting is appropriate in other situations, such as important medical events that may not be immediately life-threatening or result in death or hospitalization but may jeopardize the patient or may require intervention to prevent one of the other outcomes listed in the definition above. These should also usually be considered serious.

Examples of such events are intensive treatment in an emergency room or at home for allergic bronchospasm, blood dyscrasias or convulsions that do not result in hospitalization, or development of drug dependency or drug abuse.

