#### 11.1.2 Severity

The intensity of an AE is an estimate of the relative severity of the event made by the Investigator based on his or her clinical experience. The following definitions are to be used to rate the severity of an AE:

- Mild: The adverse event is transient and easily tolerated.
- Moderate: The adverse event causes the patient discomfort and interrupts the patient's usual activities.

- **Severe:** The adverse event causes considerable interference with the patient's usual activities, and may be incapacitating or life-threatening.

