### 11.1.3 Relationship to IMP

The Investigator will establish causality of the AE to experimental treatment. The Investigator should take into account the patient's history, most recent physical examination findings, and concomitant medications.

The following definitions will be used to determine causality of an AE:

- **Not related:** temporal relationship of the onset of the AE, relative to the experimental treatment is not reasonable or another cause can explain the occurrence of the AE.
- **Related:** temporal relationship of the onset of the AE, relative to the experimental treatment is reasonable, follows a known response pattern to the treatment, and an alternative cause is unlikely.

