### 11.1.4 Reporting of AEs and SAEs

All AEs must be recorded in the case report form, defining relationship to IMP and severity. The frequency of each AE should always be recorded to indicate if the event is intermittent, continuous, one-time event etc. If the same AE occurs repeatedly at approximately the same strength in the same patient, this AE should be counted only once. If any aspect of the AE changes (including but not limited to severity, frequency, causality), a new AE should be recorded. AE start and end dates should be clearly defined in the CRF.

**As soon as the Investigator is aware of a potential SAE, he/she should report the SAE to the Pharmacovigilance (PV) CRO by fax or e-mail, and in any case no later than 24 hours after the knowledge of such a case. In case of questions regarding an SAE, the investigator or authorized study personnel can contact the PV CRO monitor by phone. The contact information, is provided in the Investigator Site File.**

At the time of the call, the Investigator must provide as a minimum requirement, the Patient number, birth date, nature of the SAE, and a preliminary assessment of causality. The Investigator should follow-up the initial notification of the potential SAE by faxing/e-mailing a copy of the form to PV CRO at the number/address provided in the Investigator Site File. The SAE reporting form should be received to the PV CRO within 24 hours after knowledge of such a case.

Follow-up information on an existing SAE that is fatal or life-threatening should be reported by the Investigator to PV CRO within 5 days after the initial report. Where appropriate, hospitalisation or autopsy reports should be made available. All SAEs will be followed up until resolution (i.e., asymptomatic, stabilisation or death).

AE's should be reported for the entire study duration up to and including the follow up period. Following completion of the study, if the Investigator becomes aware of any AE that is potentially related to the IMP, the Sponsor should be notified.

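### The trial-level safety stop and the patient discontinuation rule act on a grade and a causality judgement that the protocol's adverse-event ratings do not supply

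*Protocol*

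**What the plan says.** **The two rules that act.** Section 7.8 of the protocol is the only trial-level safety stop stated: "Trial will be stopped if more than one patient has a Grade 3 or higher AE on the CTCAE scale in any one category", where the event is judged possibly or probably attributable to study drug. Section 7.5 applies the same test to one patient: a Grade 3 or higher NCI-CTCAE event "that is determined to be possibly or probably attributable to the study drug will be discontinued". CTCAE is named only in these two sections, without a version. Neither section says who makes the attribution, and 7.8 does not say what a category is.

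**The ratings that are collected.** Section 11.1.2 introduces mild, moderate and severe with "The following definitions are to be used to rate the severity of an AE". Section 11.1.3 gives two causality levels. Not related applies when the timing "is not reasonable or another cause can explain the occurrence of the AE". Related needs reasonable timing, a known response pattern and an unlikely alternative cause. Section 11.1.4 then states: "All AEs must be recorded in the case report form, defining relationship to IMP and severity".

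**The reporting.** Section 12.8.4 promises a per-arm summary of AEs possibly or probably related to treatment. SAP Section 7.5 tabulates AEs by mild, moderate and severe intensity, with one category for AEs related to study medication. Section 11.2.1 of the protocol defines an adverse reaction by a wider standard: a reasonable possibility, meaning that the relationship cannot be ruled out.

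**The concern.** A stopping rule works only if the people applying it have its inputs. Here the rule needs a CTCAE grade and a possible-or-probable judgement, while sites are told to give an activity-based severity and a two-way causality rating. The same event can count under 7.8 and be Not related under 11.1.3.

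The rule fires at the second patient in a category, so one classification can decide whether the trial stops, and two sites can treat like events differently. No other section is stated to count non-serious Grade 3 events across sites. The medical monitor's task in 7.7 is to review protocol violations, and the interim recommendation in 12.9 rests solely on the primary efficacy endpoints.

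**Working it through.** The plan gives no operating figure for the stop, so there is nothing to reproduce. The check is a comparison of texts.

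| Input | Rules (7.5, 7.8) | Collected (11.1.2 to 11.1.4) | Reported |
|---|---|---|---|
| Severity | CTCAE Grade 3 or higher | Mild, moderate, severe | SAP 7.5: mild, moderate, severe |
| Causality | Possibly or probably attributable | Related, Not related | 12.8.4: possibly or probably related; SAP 7.5: related |
| Unit of count | More than one patient in a category | Not specified | SAP 7.5: MedDRA SOC and preferred term |

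**Severity.** No text equates Severe with Grade 3. The definition of Severe begins "The adverse event causes considerable interference with the patient" and is about usual activities. Section 7.5 itself foresees withdrawal for an abnormal laboratory result, and such a result need not interfere with activities. The SAP laboratory tables use clinical significance and normal-range shifts, not grade.

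**Causality.** Take three events with reasonable timing:

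1. Another cause can explain the event, but the drug cannot be ruled out. By 11.1.3 it is Not related. By 11.2.1, and on the ordinary meaning of *possibly* in 7.8, it is attributable.
2. There is no other cause, but no known response pattern. It meets neither definition in 11.1.3.
3. There is a known pattern and an unlikely alternative. It is Related, and it counts on every reading.

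Related is therefore narrower than the term in 7.8.

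**Consequence for 7.8.** There are two ways to operate the rule.

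- *The 11.1.3 entry is used.* Events 1 and 2 can go uncounted. If exactly two patients qualify and one is entered as Not related, the recorded count is 2 − 1 = 1, and *more than one* is not met.
- *A separate judgement is used.* The rule can work as intended, but the specified data hold neither that judgement nor the grade, so they do not show whether the trigger was met.

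**Illustration for the first route only.** Both rates are assumptions; neither is in the documents. Let p be the share of DS107 patients with a qualifying event in one category and m the share of those events entered as Not related. With 110 patients per arm (Section 12.3), the chance of reaching two is P(X ≥ 2), X ~ Binomial(110, p(1 − m)). For p = 1% and m = 0: 1 − 0.99^110 − 110 × 0.01 × 0.99^109 = 1 − 0.331 − 0.368 = 0.301.

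| Assumed p | m = 0 | m = 25% | m = 50% |
|---|---|---|---|
| 0.5% | 10.5% | 6.5% | 3.1% |
| 1% | 30.1% | 20.0% | 10.5% |
| 2% | 64.8% | 49.3% | 30.1% |
| 3% | 84.6% | 71.1% | 49.3% |
| 5% | 97.6% | 92.1% | 76.4% |

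The table shows how sensitive a two-patient rule is to miscoding. It is not an estimate for this trial.

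**The case against.** **The CRF entry need not control the rule.** A reader might infer that a Not related entry blocks the stop. The documents do not say so: 7.8 asks only that attribution be determined and does not tie it to the 11.1.3 field. This objection stands, and it is why the conclusion has two branches.

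**There is a partial trail.** When a patient is withdrawn for an event or laboratory result, "the principal specific event or test will be recorded" under 7.5, and the SAP tabulates and lists AEs leading to discontinuation. A reader might suppose that this trail ends with treatment. It does not: the SAP category is discontinuation from the study, which can happen during follow-up. The trail is still not specified to hold grade or the attribution judgement.

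**Other safeguards exist.** Serious events go through SUSAR reporting, and of important medical events 11.1.1 says "These should also usually be considered serious". Investigators review laboratory results and may withdraw any patient. These narrow the gap, but none is stated to count non-serious Grade 3 events across sites.

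**The SAP table can be produced.** A single related category can be filled from the 11.1.3 ratings. That is true, but it is not the summary that 12.8.4 describes.

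**Category may be clear.** Because the word follows the mention of the CTCAE scale, a CTCAE category is the natural reading. The level still needs naming.

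**Earlier studies.** A reader might take the severe SAEs rated unrelated in Phase 2b, or the CPK exception in a topical study, as signs that countable events are being lost. Nothing suggests those SAEs were possibly attributable, and that study's causality scale is not given. The direction of the CPK difference is not stated, and oral Phase 2a reported no drug-related AEs associated with laboratory results.

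**Conclusion.** The inconsistency is real and should be fixed. Confidence is high that 7.5, 7.8 and 12.8.4 use terms that 11.1.2 to 11.1.4 neither define nor record, and that Related in 11.1.3 is narrower than both 7.8 and 11.2.1. Confidence is lower about the practical effect, for two reasons: the AE page is not in the documents and may already hold grade and a finer causality field, and the way attribution is determined for 7.8 is not stated.

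The size that can be stated from the documents is that one classification can decide a two-patient trigger. Without an event rate or a miscoding rate, no probability can be attached to this trial. A reader might go further and conclude that the stop cannot work, or that the efficacy results are compromised. The documents support neither. A separate, well-run attribution process would satisfy 7.8, and the primary endpoints, estimand and power do not depend on it.

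**What to change.** 1. Record CTCAE grade, with the version stated, for every AE including laboratory AEs, alongside the 11.1.2 rating. Do not let Severe stand in for Grade 3.
2. Keep the two-level causality scale, but redefine Related in 11.1.3 as a reasonable possibility that cannot be ruled out, matching 11.2.1, with Not related as its complement. Use that term in 7.5, 7.8 and 12.8.4. SAP 7.5 already works with a single related category, so a longer causality scale is not needed.
3. State in 7.8 that category means a CTCAE category, name the level, and say that the medical monitor keeps the count across sites.

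The cost is a protocol amendment, with authority and ethics submission if it is substantial (Section 13.1), and one grade field if the AE page lacks it. No visit or procedure is added, but the medical monitor takes on a running count. AEs already recorded may need re-rating so that the trial does not end with two causality standards. The wider definition will raise the number of AEs reported as related, and the report should say so. If the AE page already captures grade and possible attribution, only the wording needs aligning.

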## 8 STUDY CONDUCT

### 8.1 Study Schedule

Patients will come to the clinic on 8 occasions: at Screening/Visit 1, Baseline/Visit 2, Week 4/Visit 4, Week 8/Visit 5, Week 12/Visit 6, Week 16/Visit 7 (end of treatment), Week 18/ Visit 8 (follow up) and Week 20/Visit 9 (follow-up). A telephone visit will also be performed at Week 1/Visit 3.

Patients who discontinue the study early will be asked to attend the investigative site as soon as possible so that assessments scheduled for Visit 7 can be conducted at an Early Termination visit.

In the event that treatment is occurring, a wash out period of up to 4 weeks may be necessary. At the Screening Visit, after giving informed consent to participate, patients will be assessed using the screening examinations. Eligible patients with confirmed AD using the American Academy of Dermatology Consensus Criteria and who meet all the inclusion criteria and do not meet the exclusion criteria at the baseline visit will be enrolled.

During the treatment period and follow-up period patients will be restricted from using any other treatment for AD, with the exception of the same emollients they have been consistently using since the screening visit. A tabulated flow chart of the study is presented in Appendix 1 (Section 15.1).

